Primary Endpoint	
The primary study objectives are as follow:
 
 1) Change in gait speed (m/s) from baseline to study completion (90 days following discharge from acute care or earlier if study participant withdraws); 2) time-to-functional change in gait speed from baseline to study completion 3) adherence to the MR-Stride Plus therapy schedule.
Secondary Endpoint	
The secondary study objective is to assess the median length of stay in acute stroke hospital and the percent of readmission during the 90 (+/-7) days following discharge.

Participant Population	
No age, race, education or geographical restrictions apply. All individuals who meet the inclusion/exclusion criteria at participating study sites will be considered.

Inclusion Criteria	
To be enrolled and randomized into the study, potential Study Participants must meet all of the following inclusion criteria:
 
 1.0 Must be 18 years of age or older. 2.0 Must be able to read and speak English fluently. 3.0 Be within 24 hours from admission for confirmed stroke event.

	
4.0 Currently able to walk at a speed greater or equal to 0.4m/s, but less than 1.0m/s, as determined by a 6-meter walk test (approximately 20 feet) for comfortable walking speed (the average of three trials).
 
5.0 Demonstrates some level of asymmetry in gait.
 
6.0 Is expected to be discharged from the acute care setting requiring physical therapy per standard of care and participant has verbally committed to receiving at least one therapy session.
 
7.0 Able and willing to consent with proposed study schema (verbal commitment), including consent to participate in communication with the treating clinician (as needed) during the study period.
 
8.0 Score ≤1 on question 1b and a 0 on question 1c on the NIH Stroke Scale.
 
9.0 Able to safely participate in protocol-defined walking therapy sessions of 30-minute duration as determined by the Investigator.

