Procedures	
ARM A: STANDARD OF CARE + MR-STRIDE PLUS
 
For Study Participants randomized into Arm A, therapy sessions will begin within twenty-four (24) hours of enrollment. Intervention Phase 1 of the study requires a minimum of one (1) therapy session with the possibility of additional sessions until discharge; however, no more than 3 therapy sessions should occur during a given week. Intervention Phase 2 of the study requires 3 independent, remote therapy sessions a week regardless of discharge setting (e.g., rehabilitation hospital or home). Therapy will continue until day 90 (+/-7) following discharge from acute care. Therapy sessions with the MR-Stride Plus should not replace standard of care physical therapy, but be used in addition to standard of care physical therapy.
 
Participants may be contacted by the study staff to collect data on the number of standard of care physical therapy services provided and occurrence of readmission to acute care.
 
Participants will be able to schedule their three (3) sessions a week therapy according to their needs. Participants will be allowed to miss sessions if they are unable to make them up on a different day in the week. Participants therapy activity will be monitored remotely by the study team. If participants are unable to maintain the therapy schedule, the study will contact the participants to gauge willingness to continue. At investigator discretion and participant agreement, the number of sessions a week may be reduced or the participant may withdraw from therapy. If the participant is withdrawn from therapy, participants will be asked if they are willing to participate in a gait speed assessment using the MR-Stride Plus at day 45 and 90 post-discharge if they have not already been completed.
 
The 6-meter walk test (approximately 20 feet) will be conducted to evaluate gait speed at screening and biweekly thereafter until study completion. Gait speed will also be assessed at

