Minimizing Bias	The study is not blinded because the primary outcome measure of gait speed renders the likelihood of a placebo benefit unlikely. However, Study Participants will be blinded to the results of the 6-meter walk test (approximately 20 feet). No results will be provided to the Study Participant at any time during participation in the trial.
Study Visits	All key assessments will be conducted at the study site and remotely via telecommunication, as applicable.
Study Duration	Each Participant is required to complete a screening visit. For Participants who are randomized into Arm A (MR-Stride Plus Intervention), therapy sessions will take approximately forty-five (45) minutes for set-up and therapy. After the first therapy session in

	
the acute care setting, participants should be able to complete the setup and therapy session with the MR-Stride Plus independently. Collection of data related to study adherence (for participants in the MR-Stride Plus Intervention), gait speed assessment, standard of care administration, discharge and readmission will be performed by study staff remotely through review of medical records, MR-Stride Plus database, and by contacting the participant over the phone. Once participants have reached 90 days following discharge from the acute care facility for the initial stroke event, no follow-up or subsequent Participant involvement is required.

Study Discontinuation, Drop Out, Withdrawal and Replacement	
Participants may discontinue their participation in the study at any time. A Participant may be withdrawn from the study at any time at the discretion of the Investigator.
 
Participants who are withdrawn or drop out prior to the study endpoint will still have data that was collected up until the withdrawal/drop out eligible for analysis. These Participants will be analyzed in an Intent-To-Treat analysis.

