	
Muscle strain/tear; Injury due to fall : Injuries such as muscle strains and tears are also possible due to exercise activities. Injuries due to falling are also possible.
 
Abnormal physiological response; Irregular heart rate; Fainting: As with any exercise, there is the possibility that abnormal responses could occur. These abnormal responses include unexpected changes in blood pressure, irregular heart rate, fainting, or joint injury. This risk is increased in the post stroke population.
 
Bruising and bleeding : Participants who are taking anticoagulants may be at increased risk for bruising and bleeding due to a fall.
 
Rare Risks:
 
 • Heart problems • Hospitalization • Anxiety • Heart attack • Stroke • Death 
Heart and lung problems; Hospitalization: As with any exercise, there is the possibility that abnormal responses could occur. Rare risks associated with exercise could include heart problems or hospitalization and in very rare cases, stroke and death. There is also a risk of pulmonary embolism.
 
Anxiety : There also is a potential risk for Study Participants to become anxious.
 
Many of the investigators are licensed physical therapists and most study staff and students have training in CPR and first aid. All of the aforementioned risks will also be mitigated through the following:
 
 • Potential Study Participants will be provided with the consent form and be provided ample time to read it and ask questions. The research team will address any concerns. Study Participants will be told that participation in the study is completely voluntary and they have the right to withdraw from the study at any time. • Adequate rest periods and water will be encouraged to optimize comfort and reduce fatigue. • Total walking time per therapy session will be limited to one half hour. • Trained investigators may monitor vital signs and check for symptoms of distress during the initial therapy session with the MR-Stride Plus. Any findings out of the ordinary will be reported to the participant's primary healthcare provider or emergency services should they require medical attention. 
All participants are free to end testing or procedures that cause anxiety or discomfort at any time, this will not affect any remuneration or transportation they are entitled to.

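### The reason given for not blinding is unsound for a self-paced walk, and nothing guards the assessment of gait speed against knowledge of the arm

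*Protocol*

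**What the plan says.** The first primary objective is "Change in gait speed (m/s) from baseline to study completion", and the second, time to functional change, is built on the same measure (Protocol, Primary Endpoint). Minimizing Bias gives the only reason for an open design: "The study is not blinded because the primary outcome measure of gait speed renders the likelihood of a placebo benefit unlikely". The only safeguard offered is that "Study Participants will be blinded to the results of the 6-meter walk test".

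The pace of the walk is described once, in Inclusion Criterion 4.0, where eligibility is set "as determined by a 6-meter walk test (approximately 20 feet) for comfortable walking speed (the average of three trials"), with an entry range of 0.4 to below 1.0 m/s. For follow-up in Arm A, Procedures states: "The 6-meter walk test (approximately 20 feet) will be conducted to evaluate gait speed at screening and biweekly thereafter until study completion". Arm B has the same named test at baseline and every two weeks after discharge. Study Design, however, has Arm A perform a Day 90 walking test with the study device.

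The Investigational Device Description presents the device as intended to improve walking speed. Arm B receives standard of care without it, and no sham is described. The Protocol does not say who times the 6-metre walk.

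**The concern.** The stated reason credits gait speed with a resistance to expectation that a comfortable-pace test does not have. A person who chooses how fast to walk, and knows they were given a device to walk faster, can walk faster on the day without any change in capacity. Withholding the results does not help, because any influence acts during the walk and the participant already knows the arm.

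The reason also covers only placebo response in the participant. It gives no ground for leaving the person who instructs and times the walk aware of the arm, and no provision is made for that person.

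Two of the three primary objectives rest on gait speed. A shift from expectation or handling would be expected to favour the device, and the planned contrast would not distinguish it from a treatment effect.

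**Working it through.** The Protocol gives no figure on this point to reproduce, so the check is first one of reasoning and then an illustration of scale.

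**1. Does the stated reason fit the measure?**
- Pace: comfortable, for eligibility (Inclusion Criterion 4.0). Carrying this to follow-up is an inference from the same named test; the Protocol does not state it.
- Knowledge of arm: open to participants. Arm A has the device; Arm B has standard of care only.
- Safeguard: test results are withheld from participants. This conceals the arm from neither participant nor tester.
- Assessor: not named, and not covered by the reason given.

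The reason therefore does not establish that expectation is unlikely to matter, and it leaves the assessor out.

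**2. How sensitive is a 6-metre walk?** The distance is from the Protocol. The shift d of 0.3 to 0.5 s is an assumption, and it must be systematic and differ between arms. A walk at true speed v takes 6/v seconds. If it is completed, or timed, d seconds faster, the change in measured speed is 6/(6/v − d) − v.

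| v (m/s) | 6/v (s) | d = 0.3 s | d = 0.5 s |
|---|---|---|---|
| 0.4 | 15.0 | 6/14.7 − 0.4 = 0.008 | 6/14.5 − 0.4 = 0.014 |
| 0.6 | 10.0 | 6/9.7 − 0.6 = 0.019 | 6/9.5 − 0.6 = 0.032 |
| 0.8 | 7.5 | 6/7.2 − 0.8 = 0.033 | 6/7.0 − 0.8 = 0.057 |
| 1.0 | 6.0 | 6/5.7 − 1.0 = 0.053 | 6/5.5 − 1.0 = 0.091 |

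The change is small at the bottom of the entry range and grows with speed. The 1.0 m/s row lies at the entry ceiling, so it describes participants who have improved by follow-up.

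**3. What could a shift do with 20 per arm?** The arm size is from Study Design. The SD of change (0.15 to 0.30 m/s) and a two-sided 5% test are assumptions. With SE = SD × √(2/20) and bias b, the chance of rejecting when there is no true effect is Φ(b/SE − 1.96) + Φ(−b/SE − 1.96). For b = 0.05 m/s and SD 0.20, SE = 0.0632 and b/SE = 0.79, so the chance is about 12%. Across the SD range it runs from 18% (SD 0.15) to 8% (SD 0.30). This shows scale only; nothing in the Protocol says that a bias of this size exists.

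**The case against.** An open design is reasonable. Participants cannot readily be masked to a music-cue device compared with usual care. That stands: the fault lies in the reason given and the missing assessor safeguard, not in being open-label.

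A reader might infer that staff bias is built into the outcome. The documents do not support that. No timer is named, visits to the facility are not required after discharge, gait-speed data are partly gathered from records, the device database and telephone contact (Study Duration), and Arm A's Day 90 test uses the device, whose sensors record speed. Where sensors measure the walk, stopwatch handling does not arise, although that applies to Arm A alone.

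A reader might also infer that half a second explains most or all of a worthwhile effect. That does not hold across the entry range: it adds 0.014 m/s at 0.4 m/s and 0.032 at 0.6. The Protocol gives neither a timing error nor a worthwhile effect. The shift would also have to differ systematically between arms and survive any averaging of trials. If the screening test serves as baseline, it precedes randomization and is not exposed; a shift would then enter only at follow-up.

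Finally, the Protocol says only that a placebo benefit is unlikely, which is a judgement, and the documents hold no measurement of expectation effects on gait speed. The supportable criticism is that the reason is unsound, not that a placebo effect has been shown. Masking of the analyst is commonly left to an SAP, which is not at hand, and is not part of this point.

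**Conclusion.** The point holds in a limited form. The sole reason given for an open design does not fit a walk at a self-chosen pace with no sham control, does not address the assessor, and is paired with a safeguard that masks neither participant nor tester to the arm. Expectation and assessor bias on two of the three primary objectives are unguarded risks; neither is demonstrated.

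The scale depends on walking speed: under the assumed 0.3 to 0.5 s shift, from about 0.01 m/s at the lower entry limit to between 0.05 and 0.09 m/s at 1.0 m/s. The conclusion about the rationale does not depend on those assumptions. It does rest on the inference that follow-up walks use the comfortable pace stated for eligibility. The Protocol should be changed, because the remedy is cheap.

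**What to change.** - In Minimizing Bias, replace the claim about placebo benefit with a statement that the trial is open-label because participants cannot readily be masked to the device, and that gait speed may be affected by expectation.
- For the 6-metre tests already scheduled and used for the primary endpoint, fix one procedure for both arms: one script, comfortable pace, mean of three trials, and no music, cue or encouragement.
- Reconcile this with Study Design, where Arm A's Day 90 walk is done with the device while Arm B does the 6-metre walk.
- Where the walk is observed in person or live by video, have it timed by an existing staff member who does not run or monitor that participant's device sessions and is not told the arm. Otherwise report it as an unmasked assessment.

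The cost is Protocol wording and assignment of staff already on the study; no participants or visits are added. The drawbacks are some scheduling effort, limited masking for remote tests, and some participants revealing their arm.

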	
the time of withdrawal from study therapy if withdrawal occurs before Day 90 (+/-7) post discharge.
 
At the initial therapy session, Study Participants will be provided with all necessary equipment (pre set-up) and instruction for using the MR-Stride Plus. Study staff will provide appropriate oversight of the Participant during their initial walking therapy session in acute care to ensure safety; study staff will not be required to provide any instruction on use of the device. Participants will conduct 30 minutes of walking therapy at the participant's self-selected pace in a space (e.g., track or hallway) that limits the amount of stops and/or pivot turns in order to optimize velocity. Participants may choose to take breaks as needed, or when investigators believe that a rest break is necessary. The use of an overhead harness system is prohibited in this study. If technical or medical issues arise, the training session should be terminated to allow for adequate resolution.
 
For independent, remote therapy sessions following discharge from the acute care hospital, it is not required that a participant be under the supervision of clinical staff or a caregiver (depending on discharge setting), but participants may choose to according to their preference. Participants should perform their therapy sessions in an environment that limits safety hazards and, in a space, e.g., track or hallway, that limits the amount of stops and/or pivot turns in order to optimize velocity. Participants will perform their 30 minutes of walking therapy at their self-selected pace.
 
MR-Stride Plus Procedure: Study staff and participants will be required to follow the Instructions For Use (IFU) provided by MedRhythms. The IFU will detail all procedures required for proper operation of the system. Study Participants will be trained in utilizing the Stride Plus by the study staff. Mobile devices that have the MedRhythms Stride Plus application installed will be provided for use during therapy sessions. Participants will be provided with a pre-established username and password. No personally identifiable patient information will be recorded or stored in the Stride Plus application.
 
ARM B: STANDARD OF CARE
 
For Study Participants randomized into Arm B, clinical standard of care will be followed with no intervention provided using the MR-Stride Plus. Participants will also complete the 6MWT at screening, baseline and biweekly post-discharge from acute care and at days 45 and 90 (+/-7 days) following discharge.
 
All participants will be followed for 90 days following discharge from acute care facility for initial stroke event and discharge date, discharge setting, number of physical therapy services and occurrence of readmission to acute care will be collected.

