Benefits / Risks	
Benefits
 
This project will facilitate the development and clinical translation of targeted gait interventions that can improve walking ability, including the development of new technology that extends the abilities of clinicians.
 
Risks
 
There are some risks to participating in this study. We have categorized them below as Possible, Less Likely, and Rare risks. In summary, the expected risks include:
 
Possible risks:
 
 • Fatigue • Nausea • Shortness of breath • Muscle or joint soreness • Minor muscle cramps • Loss of balance or fall 
Fatigue; Muscle or joint soreness – Depending on participants' level of disability, sessions will be mildly to moderately strenuous. The participant may become fatigued, or experience joint soreness in their hip, knee, ankle or foot.
 
Fatigue; Nausea; Shortness of breath; Muscle cramps or muscle soreness – As with any exercise, there is the possibility that abnormal responses could occur. These include nausea, shortness of breath, fatigue, muscle cramps or soreness (lasting into subsequent days after testing).
 
Loss of balance or fall:
 
There is a risk of falling to the ground. Participants who typically wear an ankle brace may be asked to walk without the brace. When walking without the brace, the foot and ankle may not be as stable and there is an increased risk of ankle sprains during walking and falling.
 
Less Likely Risks:
 
 • Muscle strain/tear • Injury due to fall (ankle sprain, twisted knee, etc.) • Abnormal physiological response to physical activity • Irregular heart rate • Fainting • Bruising and bleeding

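### The protocol discloses that habitual ankle-brace users may be asked to walk without the brace, at added fall risk, but no listed procedure needs this and nothing limits when it may be asked

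*Protocol*

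**What the plan says.** Under Benefits / Risks, in the paragraph on loss of balance or fall, the protocol says: "Participants who typically wear an ankle brace may be asked to walk without the brace". The next sentence gives the consequence: "the foot and ankle may not be as stable and there is an increased risk of ankle sprains during walking and falling". A little further on, under bruising and bleeding, it notes: "Participants who are taking anticoagulants may be at increased risk for bruising and bleeding due to a fall".

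The risk section then turns to mitigation. It cites staff background ("Many of the investigators are licensed physical therapists and most study staff and students have training in CPR and first aid") and introduces a list with "All of the aforementioned risks will also be mitigated through the following". One item reads "Trained investigators may monitor vital signs and check for symptoms of distress during the initial therapy session with the MR-Stride Plus". The section closes with a right to stop: "All participants are free to end testing or procedures that cause anxiety or discomfort at any time". Procedures (Arm A) adds: "Study staff will provide appropriate oversight of the Participant during their initial walking therapy session in acute care to ensure safety".

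**The concern.** The protocol describes something the study itself might do, namely ask a participant to take off a support, and says that this makes a fall or sprain more likely. An added risk of this kind normally comes with a named procedure and a reason. Here there is neither, so staff have no guidance on when such a request is proper, and an ethics reviewer cannot weigh the risk against a purpose.

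Only participant safety is at stake. The population has had a recent stroke, and some will be on anticoagulants, for whom the protocol itself says a fall carries more risk of bruising and bleeding.

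**Working it through.** No arithmetic in the plan bears on this point, so the check sets the texts side by side.

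**Step 1. Where a brace is mentioned.** The word occurs twice in the first brace sentence and once at the start of the next: 2 + 1 = 3 mentions, all in the fall-risk paragraph. It occurs nowhere else in the protocol.

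**Step 2. Whether any procedure needs brace-free walking.**

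- Inclusion criterion 4.0: a 6-meter walk at comfortable speed, mean of three trials, with a result of at least 0.4 and below 1.0 m/s. No brace condition.
- Procedures, Arm A: the 6-meter walk at screening and every two weeks, plus a gait-speed assessment at withdrawal from therapy. No brace condition.
- Study Design: walking tests with the device at discontinuation and at Day 90. No brace condition.
- Procedures, Arm B: walk tests at screening, baseline, every two weeks, and Days 45 and 90. No brace condition.
- Therapy sessions, in hospital and remote: 30 minutes at the participant's own pace in a space with few stops or turns. No brace condition.
- Exclusion Criteria: criterion 4.0 covers a lower-limb prosthesis. No criterion covers a brace or orthosis.
- Operation of the device is left to the manufacturer's instructions for use, which are not shown.

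No procedure written in the protocol requires removal of a brace, and none rules it out.

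**Step 3. Whether a safeguard governs the request.**

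- At entry: the investigator judges whether the participant can walk safely for 30 minutes (inclusion 9.0), the speed must be at least 0.4 m/s (4.0), and recent orthopedic surgery and co-morbidities that prevent exercise are excluded (exclusions 6.0 and 7.0).
- In sessions: staff oversee the first one, rest breaks may be called by participant or investigator, a session stops if a medical problem arises, and remote walking should be done where hazards are limited.
- In the mitigation list: four items (consent and withdrawal; rest and water; the half-hour limit; optional checks at the first session). None of the four mentions a brace.
- Under Compliance: adverse events are recorded, and the study halts if an event involving risk to participants is suspected.

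These safeguards are real but general. None says when a brace may come off or confines such a request to supervised walking.

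**Step 4. Size.** Expected extra events = (number of brace users) × (brace-free walks per user) × (added risk per walk). The protocol gives none of the three factors, so no figure can be derived. The first factor is probably small, because enrolment is within 24 hours of admission. It need not be zero: exclusion 2.0 exempts stroke from the bar on earlier neurologic injury, so a brace user from a previous stroke could enter. A brace could also be fitted during the 90 days after discharge.

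**The case against.** The strongest reply is that this is a risk disclosure and nothing more. It sits in the risk section, its wording is permissive, and what participants actually do is set elsewhere, where no step asks for brace removal. It may simply be over-inclusive wording. A participant who is asked may decline. The instructions for use, which staff and participants must follow and which concern sensors worn on the shoes, could contain the reason.

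Much of this stands. The protocol does not direct anyone to walk without a brace, and the unseen instructions may bear on it. Counting mitigation items that omit the word also proves little alone, since those items name few specific risks. But the reply does not leave the text sound. If nobody will make the request, the statement is not needed. If somebody will, the procedure and its limits are missing. The instructions for use govern operation of the device, whereas the disclosure speaks of participants in general and the walk tests apply to both arms.

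A reader might infer more: that the ban on an overhead harness and the absence of required supervision in remote sessions expose brace users to unsupported, unsupervised walking without a brace. The protocol does not support that. It links neither provision to braces, and nothing says that anyone would ask for brace removal in a remote session.

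**Conclusion.** The point holds as a minor safety matter. The protocol discloses a request that it says raises the risk of sprains and falls, gives no purpose for it, needs it in no listed procedure, and sets no limit on when it may be made.

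Three further inferences should not be drawn. The protocol does not instruct brace removal. It does not lack safeguards; it lacks one specific to this act. And although gait speed is a primary endpoint and no brace condition is fixed, nothing in the document shows that brace use would differ between arms or visits, so no bias is claimed.

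The conclusion rests on the protocol text alone. It assumes that the instructions for use do not already require and regulate brace-free walking. If they do, the remedy is to name that step in the protocol.

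**What to change.** Replace both brace sentences in the fall-risk paragraph, since deleting only the first would leave the second without a referent. In Procedures, for both arms, state that participants wear the brace or orthosis their treating clinician currently prescribes at all gait tests, including screening and baseline, and at all therapy sessions.

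First check the instructions for use. If they or a specific test truly require brace-free walking, keep the risk disclosure, name the step and its purpose, and allow it only in person under clinical staff supervision. As no study visit to the facility is required after discharge, that would in practice mean the acute-care stay.

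The cost is one protocol amendment, matching consent wording if the statement appears there, one institutional review board submission, and the check against the instructions for use. No visit or test is added.
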